Mounting evidence from epidemiological studies indicates that serum UA levels are strong risk factors for the development of chronic kidney disease and loss of kidney function among persons with T1D. Prospective data from the Second Joslin Kidney Study (JKS) identified elevated baseline serum UA as one of the strongest independent predictors of early GFR loss among T1D persons with microalbuminuria and normal renal function at baseline.⁸ The unadjusted odds ratio of developing increased GFR loss was 1.5 (95% CI 1.3-1.9, $p=0.0002$) for each mg/dl increase in serum UA. This translates into a ~2.4-fold increase in the risk of early GFR loss for UA levels ≥ 4.5 mg/dl as compared to UA levels <4.5 mg/dl. The magnitude of this effect did not significantly change after adjustment for urinary AER, gender, HbA1c, or, importantly, baseline GFR. The U. of Colorado group also found that serum UA predicted the transition from normoalbuminuria to micro- or macro-albuminuria as well as the progression of subclinical atherosclerosis in the CACTI study.^{9,10} As in the JKS, the effect of UA was not influenced by adjustment for other baseline variables. An association between UA and development of persistent macroalbuminuria has also been reported by the Steno group. It is very important to note that, in that study, the UA levels shortly after the onset of T1D was a significant independent predictor of macroalbuminuria 18 years later (hazard ratio 1.90 per mg/dl increase in UA level; $p=0.04$)¹¹, this being suggestive of a pathogenetic role.

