 - a. Untreated group = 3 ml/min/1.73 m² per year. This estimate is based on data from the Joslin Kidney Study (JKS), in which the median GFR loss among 43 subjects meeting the above criteria was 3.1 ml/min/1.73 m² per year, with 70% of subjects having a GFR loss $>$ 1.5 ml/min/1.73 m² per year. Also, among 116 subjects from Steno who met the albuminuria and GFR criteria, but for whom serum uric acid values were not available, the median GFR loss was 3.3 ml/min/1.73 m² per year, with 71% of subjects having a GFR loss $>$ 1.5 ml/min/1.73 m² per year.
 - b. Treated group = 2 ml/min/1.73 m² per year. The average GFR loss in the JKS subjects with serum UA $<$ 4.5 mg/dl was 1.5 ml/min per year. On this basis, we conservatively assumed that the allopurinol treatment, if effective, would decrease the GFR loss to 2 ml/min per year (a 33% decrease compared to the untreated group).

2. Standard deviation (SD) of residual error = 10.1 ml/min/1.73 m². This was estimated based on the root-mean-squared error from a regression model with eGFR at 3 yrs as the dependent variable and baseline eGFR as the independent variable fitted to data concerning T1D patients from the Joslin Kidney Study meeting the PERL inclusion criteria.

Assuming a two-sided alpha error equal to 0.05, the effective sample size needed to detect the pre-specified treatment effect ($\delta = 3$ ml/min/1.73 m²) at washout adjusted for baseline iGFR with 80% power is equal to n=180 per group. To take into account the anticipated overall dropout rate (up to 5%/yr or 15% over the entire duration of the study) and drug discontinuation or non-compliance in the treatment group (up to 2%/yr or 6% over the entire duration of the study), and to maintain the desired

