6.4. Baseline covariates

The following is a description of the baseline covariates that will be used in the various analyses outlined in the remainder of Section 6.

- Stratifying variables
 - serum uric acid (sUA) at baseline with 2 levels (≤ 6.0 and > 6.0 mg/dl)
 - glycated hemoglobin (HbA1c) at baseline with two levels (≤ 7.8 and $> 7.8\%$)
 - clinical site/study center with 16 levels (based on main sites with satellite sites collapsed into main sites)
- Baseline iGFR measured at Visit 4
- Baseline eGFR measured at Visit 4
- Treatment group with two levels (Allopurinol, Placebo)
- Albuminuria status with 2 levels (subjects who qualified by ACR or AER or were albuminuric at baseline vs. subjects who qualified by eGFR slope and were normoalbuminuric at baseline)
- Baseline AER geometric mean (at Visits 3 and 4 combined) expressed on log to base 10 scale

As of Dec. 17, 2018, we have complete data available for baseline serum uric acid, treatment group, and study center. The number of missing values for the other baseline covariates is 1 for iGFR, 2 for HbA1c, and 17 for albuminuria status. Missing baseline data will be imputed according to the approach described in Section 6.5. When creating covariates for analytical and imputation purposes, we will aggregate clinical sites with a small number of randomized subjects, such as Edmonton (site #11, n=3) and Vancouver (site #16, n=11) will be combined with Calgary (site #10, n=20) in the same geographic region. Similarly, Spokane (site #15, n=5) will be combined with Seattle (site #13, n=35).

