6.5. Missing values

Missing values both for baseline characteristics and for outcomes/endpoints of interest are inevitable, especially in studies with longer follow-up. To effectively address missing values that occurred for baseline covariates and for post-randomization variables of interest, and the necessity to consider post-ESRD iGFR values as an unfavorable outcome, models involving direct likelihood methods are difficult to implement. For this reason, we will perform the analyses using a *multiple imputation* (MI) approach consisting of three steps:

Step 1. Using an *imputation* model, create multiple datasets with missing values imputed

Step 2. Fit *substantive models* described in Sections 6.6 and 6.7 using imputed datasets created in Step 1

Step 3. For each substantive model, combine the results obtained in Step 2 for the inference using Rubin's rule (Rubin, 1987).

To create imputed datasets in Step 1, we will employ multivariate imputation by means of fully conditional specification (FCS) method introduced by van Buuren et al, 2006. This method is especially attractive in our case because it handles non-monotone patterns of missingness, and arbitrary types of imputed variables, i.e. both continuous and categorical. The imputation model will include baseline covariates listed in Section 6.4. In addition, to make imputation model more general than substantive models, we will include HbA1c at Visit 1 and geometric mean of AER at Visit 3 and 4 expressed on logarithmic base to 10 scale predictive of other baseline covariates.

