6.6.1. Primary analysis for the primary estimand

The goal of the primary analysis for the primary estimand is to test the null hypothesis of the difference in means between treatment arms in the primary endpoint (iGFR at the end of the 2-month wash-out period [Visit 17] following the 3-year intervention) being equal to zero. The analysis will be performed in a multiple imputation framework on the intention-to-treat (ITT) population and will employ a linear model for correlated errors with general/unstructured covariance matrix (Molenberghs and Verbeke, 2005; [name] and Burzykowski, 2013) as a substantive model. For each time t ($t = 1, 2, 3$) corresponding to post-randomization iGFR visits, i.e. visits V11 (80 weeks), V16 (156 weeks), and V17 (164 weeks after randomization) the model equation is specified as:

$$iGFR_{it} = \beta_{0t} + \beta_{1t} TRT_i + \mathbf{x}'_i \boldsymbol{\beta} + \epsilon_{it}, \quad (6.1)$$

where $iGFR_{it}$ is the value of iGFR at time t for subject i ($i = 1, \dots, 530$). Fixed effects β_{0t}, β_{1t} for $t = 1, 2, 3$ denote visit-specific intercepts and treatment effects. TRT_i is

treatment group (equal to 1 for the allopurinol and 0 for placebo). Stratifying variables (serum uric acid, HbA1c, study center), and baseline covariates: albuminuria status, AER, iGFR for subject i are included in a vector \mathbf{x}_i of p covariates (x_1, \dots, x_p) and associated fixed effects are stored in vector $\boldsymbol{\beta} = (\beta_1, \dots, \beta_p)$. We assume that residual errors ϵ_{it} ($t = 1, 2, 3$) for subject i are normally distributed with zero mean and 3×3 general/unstructured variance-covariance matrix. The model specified in (6.1) will yield the estimates of visit-specific treatment effects $\beta_{11}, \beta_{12}, \beta_{13}$ for all three visits V11, V16 and V17. In the context of the primary analysis of the primary endpoint, we are interested in parameter β_{13} , representing treatment effect at Visit 17 adjusted for stratifying variables and baseline covariates. The Kenward-Roger approximation will be used to estimate denominator degrees of freedom.

Estimand	Primary estimand defined in Section 5.2.1
Analysis	Primary Analysis of the Primary Endpoint: iGFR at the end of the 2-month wash-out period (Visit 17)
Analysis Set	ITT Population
Methods	Linear model for repeated measures with correlated errors using multiple imputation technique.

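### The primary model is valid, but by leaving out Visit 4 eGFR and using HbA1c and uric acid only as two-level strata it may give up a little precision

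*SAP*

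**What the plan says.** SAP 6.6.1 puts these terms in the covariate vector of equation 6.1: "Stratifying variables (serum uric acid, HbA1c, study center), and baseline covariates: albuminuria status, AER, iGFR for subject" i. The table in the same section shows that baseline iGFR and log10 AER enter as continuous terms. The ANCOVA in 6.6.2 reuses the vector, and the subgroup model in 6.8.1 uses the same baseline covariates.

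SAP 6.4 lists "Baseline eGFR measured at Visit 4" among the available covariates. It defines the two laboratory strata as "glycated hemoglobin (HbA1c) at baseline with two levels" (cut at 7.8%) and "serum uric acid (sUA) at baseline with 2 levels" (cut at 6.0 mg/dl). Only the two eGFR analyses, 6.7.3 and 6.7.4, use baseline eGFR in a substantive model.

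For missing data, SAP 6.5 states: "The imputation model will include baseline covariates listed in Section 6.4". It then adds that "we will include HbA1c at Visit 1 and geometric mean of AER at Visit 3 and 4". So eGFR and a further HbA1c value inform the imputed values but not the adjustment.

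Protocol 11.10 treats HbA1c, uric acid and AER as GFR predictors that raise power. Protocol section 1 describes uric acid risk as a gradient from cohort data: "The unadjusted odds ratio of developing increased GFR loss was 1.5" per mg/dl.

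**The concern.** A single baseline iGFR carries measurement error. A second baseline GFR reading, even a noisier one, recovers some of the information lost to that error. Cutting HbA1c and uric acid in two keeps the contrast between strata and discards the gradient within each stratum, although the protocol itself describes uric acid risk per mg/dl. Both choices can leave residual variance in the Visit 17 comparison that data already collected could remove. What is at stake is the width of the confidence interval on the one confirmatory test. Validity is not at stake: prespecified linear adjustment for baseline values does not bias a randomised comparison.

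**Working it through.** **1. The plan's own figures.** Protocol 11.10 begins "Assuming a two-sided alpha error equal to 0.05, the effective sample size needed to detect" a difference of 3 ml/min/1.73 m², with residual SD 10.1 and 80% power: 180 per group. The two-sample normal formula gives 178 (179 with the noncentral t), so this reproduces. Inflation for 15% dropout and 6% dilution: 180/(0.85 × 0.94²) = 239.7, the stated 240. With n = 240 × 0.85 = 204 per arm and effect 3 × 0.94 = 2.82, model M1 has power .805 (stated .80). The other M1 rows of Table 1 also reproduce.

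Model M2 credits HbA1c, uric acid and AER with 10% of residual variance: SD = 10.1 × √0.90 = 9.58. That gives power .844 in the last row, against .87 printed. The full M2 column needs a reduction of about 12% to 19%. I use 9.58, which follows from the stated 10%.

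**2. Adding eGFR beside iGFR.** The documents give no measurement error for iGFR and no partial correlation for eGFR, so both error SDs are assumptions.

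- Protocol 11.10 equates 10% of residual variance with 4% of total variance. Residual is then 40% of total, and total SD = 10.1/√0.4 = 15.97 (variance 255.0).
- Let s₁ and s₂ be the iGFR and eGFR error SDs, with independent errors and a unit coefficient of outcome on true baseline GFR. The variance of true baseline GFR given iGFR is λ = (255.0 − s₁²)s₁²/255.0.
- The share of residual variance removed by eGFR is r = λ²/[(λ + s₂²) × 10.1²].
- Example: s₁ = 6, s₂ = 10. λ = 219.0 × 36/255.0 = 30.9, and r = 30.9²/(130.9 × 102.0) = 7.2%.

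| iGFR error SD | eGFR error SD 8 | 10 | 12 | 15 |
|---|---|---|---|---|
| 3 | 1.0% | 0.7% | 0.5% | 0.3% |
| 4 | 2.8% | 1.9% | 1.4% | 0.9% |
| 6 | 9.9% | 7.2% | 5.4% | 3.7% |
| 8 | 20.1% | 15.2% | 11.7% | 8.3% |

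The SE falls by 1 − √(1 − r). For iGFR error SD 3 to 6 that is about 0.2% to 5.1%. The bottom row needs an iohexol test about as noisy as some of the assumed eGFR errors, so I do not use it as representative.

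In terms of CV, with an assumed mean iGFR of 70 and eGFR error SD 11, the formula gives SE reductions of 0.2%, 1.6% and 4.9% at iGFR CVs of 4%, 7% and 10%. Simulating 530 participants, 600 trials per scenario, gave 0%, 1.3% and 4%. With continuous HbA1c and uric acid as well, the simulated total was 0.2% to 5%.

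**3. Continuous HbA1c and uric acid.** For a normal covariate with a linear effect, a median split keeps 2/π = 64% of the variance it explains. Suppose the two variables together explain q of the M1 residual variance (15% dropout, 6% non-compliance, N = 480):

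| q | Residual variance recovered | Power, two-level to continuous |
|---|---|---|
| 2% | 0.7% | .810 to .813 |
| 5% | 1.9% | .818 to .825 |
| 10% | 3.9% | .830 to .844 |

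The last row is generous: the protocol credits 10% to these two and AER together.

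**4. Effect on the primary test.** SE = SD × √(2/n), starting from M2 with 15% dropout and 6% non-compliance:

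| Further reduction r | N = 480: SE, power | N = 530: SE, power |
|---|---|---|
| 0 | 0.949, .844 | 0.903, .878 |
| 5% | 0.925, .862 | 0.880, .893 |
| 10% | 0.900, .880 | 0.857, .909 |

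**The case against.** The covariate set follows the protocol's prespecified primary model (11.3), and the two-level coding matches the randomisation strata (5.4), a standard reason for it. Baseline iGFR and log10 AER are already continuous. The protocol calls iohexol clearance accurate and reproducible and backs it with an R² threshold, re-assay and repeat tests. If the test is precise, a second GFR reading adds almost nothing. All of this stands. It is why the lower end of the range is zero and why the planned model cannot be called wrong.

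Two further arguments carry less weight. Baseline eGFR is used in the imputation, but that only informs missing values; it does not reduce the residual variance of observed Visit 17 iGFR. Protocol 11.7, reproduced in SAP Appendix I, promises sensitivity analyses on the choice of covariates, but these are exploratory, unspecified and outside the primary test.

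A reader might infer that the trial is underpowered, or that it throws away the equivalent of about 11% more participants. The documents support neither. Planned power is met without the change, and the 11% (1/0.90) is the top of a range built on assumed errors. Nor do the documents say that everyone has a baseline eGFR: SAP 6.4 declares complete data only for uric acid, treatment group and center, and gives no count for eGFR.

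**Conclusion.** The point holds as a modest refinement. Equation 6.1 and the ANCOVA that shares its covariates leave out a baseline GFR measure that the trial collects, and they use HbA1c and uric acid only in two levels. The likely gain is an SE smaller by about 0% to 5%, or roughly 0.5 to 4 power points at N = 480, mostly from eGFR. Continuous HbA1c and uric acid contribute about one point or less.

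These sizes rest on the assumed iGFR and eGFR errors, on normal covariates with linear effects, and on treating Visit 17 as a single ANCOVA, as the plan's own sample-size calculation does. The SD of 10.1 comes from eGFR regressed on eGFR, so it anchors the iGFR residual only loosely.

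**What to change.** Before unblinding, amend the SAP as follows.

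- Keep the stratification factors in equation 6.1. Add Visit 4 eGFR, continuous HbA1c and continuous uric acid, and use the same terms in the ANCOVA (6.6.2) and the subgroup models (6.8.1).
- Name one eGFR equation, since SAP 5.2.3 cites two; CKD-EPI SCr-SCysC is one choice.
- Take HbA1c and uric acid from the same visit values that were used for stratification, and name those visits, since 6.4 says only that they are baseline values.
- Carry continuous HbA1c and uric acid in the imputation model (6.5), and report the number of missing baseline eGFR values.
- Put the three new terms first in the convergence elimination order of Section 6, so that the currently planned model is the fallback.

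The cost is SAP wording and three more fixed effects in a trial of 530, with no new data. The SAP's summary of changes shows edits of similar scale (site aggregation, degrees of freedom) made just before database lock. After unblinding, the extended model should be reported only as a labelled supplementary analysis.

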6.6.2. Secondary analysis for the primary estimand

The following secondary analyses will be performed to assess how alternative assumptions of the primary endpoint (as defined above) and alternative approaches for handling missing data may affect the conclusions of the analysis:

1. Analysis of covariance using iGFR values at Visit 17 as the dependent variable and treatment effect as a covariate of primary interest. The same baseline covariates, as in the primary analysis of the primary endpoint, stored in vector \mathbf{x}_i (see Equation. 6.1) will be used in the model.

2. Performing an analysis identical to the primary one (same endpoint and substantive model) using the per-protocol analysis set rather than the ITT analysis set.

6.7. Analyses for secondary estimands

In this section we present analyses aligned with secondary estimands defined in section 5.2. Analyses will be performed using the multiple imputation technique, except those involving time-to event endpoints (sections 6.7.5, 6.7.8).

6.7.1. iGFR at the end of the 3-year treatment period (Visit 16, before the washout)

In this section we describe the analysis (estimator) aligned with the estimand for iGFR at the end of the 3-year treatment period (Visit 16, before the washout) endpoint defined in Section 5.2.1.

The least square means at Visit 16, estimate of treatment effect *at Visit 16* adjusted for baseline covariates, their 95% confidence interval and P-value will be obtained as part of the primary analysis of the primary estimand (Equation (6.1) in section 6.1.1). In the context of this secondary endpoint, we are interested in the fixed effect β_{12} , which represents the treatment effect at Visit 16 adjusted for stratifying variables and baseline covariates. To assess the hemodynamic/transient effect of the allopurinol, we will estimate the contrast $\beta_{12} - \beta_{13}$ between the treatment effect at Visit 16 (before washout) compared to that at Visit 17 (after washout).

6.7.2. iGFR time trajectory estimated from repeated iGFR measurements

This analysis is aligned with the estimand defined in Section 5.2.2

Estimand	See section. 5.2.2 for definition
Analysis	Analysis of the Secondary Endpoint: iGFR time trajectory estimated from repeated iGFR measurements.
Analysis Set	ITT Population
Methods	Linear mixed-effects model for longitudinal iGFR measures using multiple imputation technique.
Dependent Variable	iGFR measured at Visits V11 (80 weeks) , V16 (156 weeks) and V17 (164 weeks after randomization)
Model	
Fixed effects associated with:
 
 • Stratifying variables: sUA, HbA1c, study center • Treatment group • Time since randomization (in years) associated visit windows defined in section 6.3 • Time by treatment group interaction • Albuminuria status with 2 levels • Baseline AER geometric mean (at Visits 3 and 4 combined) expressed on log to base 10 scale • Baseline iGFR 
Subject-specific random effects
 
 • Random intercept for iGFR • Random slope for iGFR
Results	
 • iGFR slope estimates and 95%CIs by treatment group • Estimate of a treatment effect measured as a difference between average slopes of iGFR versus time for allopurinol and placebo groups adjusted

	for stratifying variables and baseline covariates 
 • 95% confidence interval for treatment effect • P-value for treatment effect
--	--

6.7.3. eGFR at 4 months after randomization (Visit 7)

Estimand	See section 5.2.3 for definition
Analysis	Analysis of the Secondary Endpoint: eGFR at 4 months after randomization (Visit 7).
Analysis Set	ITT Population
Methods	Linear model using multiple imputation technique.
Dependent Variable	eGFR measured at Visit V7 (16 weeks after randomization)
Model	Fixed effects associated with: 
 • Stratifying variables: sUA, HbA1c, study center • Treatment group • Albuminuria status with 2 levels • Baseline AER geometric mean (at Visits 3 and 4 combined) expressed on log to base 10 scale • Baseline eGFR
Results	
 • Least square eGFR means at Visit 7 by treatment group. • Estimate of treatment effect at Visit 7 adjusted for stratifying variables and baseline covariates • 95% confidence interval for treatment effect • P-value for treatment effect

6.7.4. eGFR time trajectory

Estimand	See section 5.2.4 for definition
Analysis	Analysis of the Secondary Endpoint: eGFR time trajectory estimated from repeated eGFR measurements using multiple imputation technique..
Analysis Set	ITT Population
Methods	Linear mixed-effects model for longitudinal eGFR measures using multiple imputation technique.
Dependent Variable	Post-randomization eGFR measured from Visits V6 through V17
Model	Fixed effects associated with: 
 • Stratifying variables: sUA, HbA1c, study center • Treatment group • Time since randomization in (in years) associated visit windows defined in section 6.3 • Time by treatment group interaction • Albuminuria status with 2 levels • Baseline AER geometric mean (at Visits 3 and 4 combined) expressed on log to base 10 scale • Baseline eGFR Subject-specific random effects 
 • Random intercept for eGFR • Random slope for eGFR
Results	
 • eGFR slope estimates and 95% CIs by treatment group • Estimate of a treatment effect measured as a difference between average eGFR versus time slopes for allopurinol and placebo groups adjusted for stratifying variables and baseline covariates • 95% confidence interval for treatment effect • P-value for treatment effect

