6.7.2. iGFR time trajectory estimated from repeated iGFR measurements	19
6.7.3. eGFR at 4 months after randomization (Visit 7).....	20
6.7.4. eGFR time trajectory	20
6.7.5. Time to serum creatinine doubling or ESRD	21
6.7.6. Urinary AER at the end of the wash-out period.....	21
6.7.7. Urinary AER during the last three months of the treatment period (Visits 15 and 16).	22
6.7.8. Time to fatal or non-fatal cardiovascular events	22
6.8. Other analyses	23
6.8.1. Subgroup analyses.....	23
6.8.2. Analyses of safety outcomes	24
6.8.3 Analyses of other measures	24
6.8.4. Analysis of the effect of post-randomization sUA changes on iGFR value at Visit 17	25
6.8.5. Time to 40% eGFR decrease.....	26
6.8.6. Time to doubling of serum creatinine, end-stage renal disease (ESRD), or cardiovascular/renal death.....	26
6.9. Model assumptions and alternative analyses	27
ACKNOWLEDGEMENTS.....	28
REFERENCES	29
APPENDIX I. Study Objective, Study Design, Outcomes & Statistical Analysis and Data Management Sections from Protocol.....	30

1. Overview

DESIGN:

- Multicenter, double-blind, placebo-controlled, parallel-group randomized clinical trial.
- N=530 total number of subjects

STUDY POPULATION:

- Type 1 Diabetes
- Inclusion/Exclusion Criteria listed in the Study Protocol

STUDY TREATMENTS:

- Oral allopurinol or placebo administered for 3 years followed by a 2-month drug washout

PRIMARY OUTCOME MEASURE:

[figure not shown]
- iGFR at the end of the 2-month wash-out period following the 3-year intervention

STATISTICAL ANALYSIS PLAN:

- This plan will be finalized prior to the database lock and unblinding of treatment groups

2. Schema

Figure 2.1. PERL Study Schema

3. Rationale for Adjustments of Statistical Analysis Plan as Compared to Protocol (Version 10, approved by DSMB on March 6, 2018)

Changes from the protocol-specified definitions of aims, outcomes, and statistical analytical approaches are outlined below. These changes reflect internal discussions since the initiation of the study that have not been incorporated as protocol amendments, but were discussed during the preparation of the Statistical Analysis Plan. These changes and the rationale for their implementation are documented herein and represent changes made prior to the database lock and unblinding of the study.

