6.1. Study populations

Two study populations will be defined for the purpose of data analysis:

- **Intention to Treat (ITT):** The ITT analysis set consists of all subjects enrolled in PERL, randomized to study medication.
- **Per Protocol:** The per protocol analysis set will consist of a subset of ITT subjects. The per protocol population will exclude subjects with major protocol deviations (defined as receiving the wrong study medication) as well as subjects for whom the average drug exposure is less than 80% (see Section 11.1 in the protocol).

To account for missing values in any specific analysis, all subjects meeting the study population definitions will be included and analyzed using (1) multiple imputation techniques (see Section 6.4), or (2) appropriate analytical approaches that allow for missing values under plausible missing data mechanisms, such as linear mixed-effects models that allow values of the dependent variable to be missing under missing at random (MAR) mechanism.

Long study follow-up results in missing values for the outcomes and precludes strict adhering to ITT principle. To mitigate this issue we will follow four strategies proposed by I.R. White et al (2011):

1. Attempt to follow up all randomized participants, even if they withdraw from allocated treatment.
2. Perform a main analysis of all observed data that are valid under a plausible assumption about missing data.
3. Perform sensitivity analyses to explore the effect of departures from the assumptions made in the main analysis.
4. Account for all ITT study population participants, at least in the sensitivity analyses.

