6.7.5. Time to serum creatinine doubling or ESRD

Estimand	See section 5.2.5 for definition
Analysis Set	ITT Population
Methods	Proportional hazards model for interval censored data.
Dependent Variable	Time to composite endpoint of serum creatinine doubling or ESRD
Proportional Hazards Model	Fixed effects associated with: 
 • Stratifying variables: sUA, HbA1c, study center • Treatment group • Albuminuria status with 2 levels • Baseline AER geometric mean (at Visits 3 and 4 combined) expressed on log to base 10 scale • Baseline iGFR
Results	
 • N(%) of subjects with doubled serum creatinine or ESRD during the course of the study • Hazard ratio of allopurinol to placebo • 95% confidence interval for hazard ratio • P-value for treatment effect

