6.7.8. Time to fatal or non-fatal cardiovascular events

Estimand	See Section 5.2.8 for definition
Analysis Set	ITT Population
Methods	Cox proportional hazards model.
Dependent Variable	Time to composite endpoint: fatal or non-fatal cardiovascular events
Cox Model	Fixed effects: 
 • Fixed effects associated with: • Stratifying variables: sUA, HbA1c, study center • Treatment group • Albuminuria status with 2 levels • Baseline AER geometric mean (at Visits 3 and 4 combined) expressed on log base to 10 scale • Baseline iGFR
Results	
 • N(%) of subjects with fatal or non-fatal cardiovascular events during the course of the study • Hazard ratio of allopurinol to placebo • 95% confidence interval for hazard ratio • P-value for treatment effect

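### SAP 6.7 exempts the time-to-event models from multiple imputation, contradicting 6.1, 6.4 and 6.5 and leaving ITT-labelled hazard models with no stated method for missing covariates

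*SAP*

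**What the plan says.** The opening of SAP 6.7 sets the rule for the secondary analyses: "Analyses will be performed using the multiple imputation technique, except those involving time-to event endpoints (sections 6.7.5, 6.7.8"). The method rows follow it. Sections 6.7.2, 6.7.3, 6.7.4, 6.7.6 and 6.7.7 each name multiple imputation. Section 6.7.5 gives only "Proportional hazards model for interval censored data" and 6.7.8 only "Cox proportional hazards model".

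Both models name the ITT population as analysis set. Both adjust for serum uric acid, HbA1c, study center, albuminuria status ("Albuminuria status with 2 levels"), baseline AER and baseline iGFR.

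On completeness, SAP 6.4 says, as of 17 December 2018, that "we have complete data available for baseline serum uric acid, treatment group, and study center". It continues: "The number of missing values for the other baseline covariates is 1 for iGFR, 2 for HbA1c, and 17 for albuminuria status". It gives no count for baseline AER.

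Three other places bear on missing covariates:
- SAP 6.1 says that, for any specific analysis, "all subjects meeting the study population definitions will be included and analyzed using (1) multiple imputation techniques", or by a second route: methods that tolerate missing values. Its example of the second route is a mixed model with missing values of the dependent variable.
- SAP 6.4, straight after the counts, sends missing baseline data to the method of 6.5. The section describes itself as covering the covariates for the rest of Section 6.
- SAP 6.5, Step 2, fits the models of 6.6 and 6.7 on the imputed datasets, with no exception.

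Sections 6.8.5 (40% eGFR decrease) and 6.8.6 (creatinine doubling, ESRD or cardiovascular/renal death) use similar ITT hazard models and do not mention imputation. The exemption in 6.7 does not name them.

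**The concern.** The multiple imputation of 6.5 is the only method in the current SAP for a missing baseline covariate. The second route in 6.1 is illustrated only for missing outcomes, which censoring already handles in a survival model; it does not help when a covariate is missing. If 6.7.5 and 6.7.8 are programmed as 6.7 reads, nothing fills the gaps in albuminuria status, HbA1c, iGFR or AER. A standard proportional hazards routine then deletes those rows without comment.

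That would cost two secondary endpoints some randomised participants and any events they had, under an ITT label. The results rows pair the number and percentage of participants with events with the hazard ratio, and the two could then rest on different sets of people. SAP 6.1 also undertakes to account for every ITT participant at least in sensitivity analyses, and none is given for these endpoints. Protocol 11.4 itself expects that events may be few, so each one counts.

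**Working it through.** The documents give no event count, sample size or power for the time-to-event endpoints, so there is no design figure to reproduce. The check is a bound on how many participants the literal reading removes, and what that does to precision.

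**Inputs.** Randomised total: "N=530 total number of subjects" (SAP, Overview). Missing: iGFR 1, HbA1c 2, albuminuria status 17 (SAP 6.4). Overlap between the three is not stated.

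**Participants removed, 6.7.5 and 6.7.8.**
- Full overlap: max(1, 2, 17) = 17; 17/530 = 3.2%; 530 − 17 = 513 remain.
- No overlap: 1 + 2 + 17 = 20; 20/530 = 3.8%; 530 − 20 = 510 remain.

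**6.8.6** has the same covariates, so the range is again 17 to 20 if it too is fitted without imputation.

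**6.8.5** has no baseline iGFR term. The range is max(2, 17) = 17 to 2 + 17 = 19 (3.2% to 3.6%).

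**Baseline AER.** It is in all four models but uncounted, so 20 is not a ceiling. Assuming that extra participants lack AER only:

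| Extra missing AER only (assumed) | Range removed | Upper end as % of 530 |
|---|---|---|
| 0 | 17–20 | 3.8% |
| 5 | 22–25 | 4.7% |
| 10 | 27–30 | 5.7% |
| 20 | 37–40 | 7.5% |

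**Precision, events lost in proportion.** The SE of the log hazard ratio scales with 1/√events, so the inflation is √(530/513) = 1.016 to √(530/510) = 1.019.

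**Precision, events lost out of proportion.** With 1:1 allocation, SE ≈ 2/√(events). Event totals are assumptions:

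| Events (assumed) | SE, none lost | SE, proportional loss at 20/530, rounded | SE, 5 lost |
|---|---|---|---|
| 20 | 0.447 | 0.459 (1 lost) | 0.516 |
| 40 | 0.316 | 0.324 (2 lost) | 0.338 |
| 60 | 0.258 | 0.263 (2 lost) | 0.270 |

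**Interaction with the fallback in SAP 6.** If a model does not fit, baseline AER and then albuminuria status are removed first. Under row deletion, removing both leaves only iGFR and HbA1c incomplete: 2 to 3 participants affected, so the analysed number moves from 510–513 to 527–528. A convergence problem would then change who is analysed as well as what is adjusted for.

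**The imputation model.** SAP 6.5 lists baseline covariates, Visit 1 HbA1c, post-randomisation eGFR, iGFR and late AER, imputed separately by arm. It contains no event indicator or follow-up time. The eGFR series carries some of the kidney outcome; nothing listed records cardiovascular events.

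**The case against.** The strongest reply is that the exemption concerns only outcomes. Event times are censored, not imputed, and 6.7 may mean no more than that, with baseline covariates still filled in as 6.4 and 6.5 direct. On that reading all 530 enter the hazard models. It is a reasonable reading, but the SAP does not state it, and the method rows that name imputation everywhere except 6.7.5 and 6.7.8 pull the other way.

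A reader might infer that these hazard ratios simply are complete-case analyses. The documents do not support that: no section says participants are dropped, and 6.1, 6.4 and 6.5 say otherwise. A reader might also extend the exemption to 6.8.5 and 6.8.6. It does not name them, and where 6.8 wants no imputation (6.8.2, 6.8.3) it says so. They are silent rather than exempt, and Step 2 of 6.5 does not reach them either, since it names only 6.6 and 6.7.

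It is also fair that the expected loss is small, that these are secondary or added endpoints, and that the documents do not show how missingness relates to outcome in either direction. All of this limits the size of the point. It does not remove the contradiction, which the analyst must settle one way or the other.

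**Conclusion.** The point holds as an internal contradiction with a default consequence. SAP 6.7 removes 6.7.5 and 6.7.8 from the only method the plan has for missing covariates, while 6.1, 6.4 and 6.5 say these data are imputed and everyone is included. Taken literally, and assuming software that deletes incomplete rows, 17 to 20 of 530 participants (3.2% to 3.8%) would leave two ITT-labelled analyses. Sections 6.8.5 (17 to 19) and 6.8.6 (17 to 20) are open to the same outcome through silence.

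These figures rest on counts dated 17 December 2018, before the August 2019 lock, and exclude any participant missing only baseline AER. Under proportional loss the SE of the log hazard ratio rises by 1.6% to 1.9%. The effect is larger only if events are few and fall disproportionately among those dropped, which the documents neither show nor rule out. The primary analysis is unaffected. This should be corrected, but it does not threaten the trial's main conclusion.

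**What to change.** In SAP 6.7, limit the exemption to a statement that event times are not imputed. In 6.7.5, 6.7.8, 6.8.5 and 6.8.6, state that the hazard model is fitted in each of the 25 datasets with baseline covariates imputed under 6.5, and that log hazard ratios are pooled by Rubin's rules. For these analyses, add the event indicator and a follow-up time term to the imputation model so that the covariates are imputed consistently with the outcome being modelled.

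If a complete-case analysis is what is intended, say so, give the analysed number beside each hazard ratio, and do not label the set ITT.

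The cost is a few lines of SAP text, a small extension of the imputation model and one pooling step. No new data are needed.
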